### 5.3.2. Guideline for significant QTcF prolongation

Significant QT interval corrected for heart rate using Fridericia 's formula (QTcF) prolongation is defined as an interval > 500 ms or an interval which increases by 60 milliseconds (ms) over baseline.

- A. If the prolongation is confirmed on a repeated ECG by **either** criterion (i.e., QTc interval > 500 ms or > 60 ms increase from baseline) the following actions will be taken:
- The subject will be monitored, treated appropriately and closely followed (ECGs at least three times per week) until the QTc interval returns to within 30 ms of baseline.
  - The Medical Monitor will be consulted prior to administering further doses or re-challenging.

If an ECG shows significant QTc prolongation the subject should be referred to a cardiologist.

- B. If the prolongation is confirmed on a repeated ECG by **both** criteria (i.e., QTc interval > 500 ms **and** > 60 ms increase from baseline) treatment with Debio 1347 should be discontinued and the following actions taken:

- The subject will be monitored, treated appropriately and closely followed (ECGs at least three times per week) until the QTc interval return to within 30 ms of baseline.

If an ECG shows significant QTc prolongation the subject should be referred to a cardiologist.

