## **RATIONALE FOR PROTOCOL AMENDMENT N° 2**

The results of an initial statistical review of pooled data showed that the antitumor activity of Debio 1347 is lower than initially assumed at the time the protocol was developed. Considering that further enrolment is unlikely to substantially change the magnitude of the efficacy observed up to now, Debiopharm decided to permanently halt the enrolment in the study after consultation with the DMC on June 10th, 2020.

Despite the lower than expected efficacy, there are ongoing subjects who are deriving benefit from the treatment, as per the opinion of their treating physician. For ethical reasons, the Sponsor intends to continue supplying study medication to these subjects until disease progression, unacceptable toxicity, subject withdrawal, or loss to follow up.

For all subjects who will remain on treatment with Debio 1347 after the implementation of Protocol Amendment N° 2, the assessments and procedures defined in the study protocol will no longer be in force and will be replaced by standard institutional care practice. Subjects must be followed regularly (at least every 2 months) to assess the potential occurrence of safety events and conduct safety laboratory analyses, as described in Table 8.1b. Only safety data will be collected in the electronic case report form (eCRF).

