13. Subjects with a known history of uncontrolled or unstable angina or myocardial infarction within the last 6 months, unstable cardiac arrhythmias despite treatment (*subjects with a history of atrial fibrillation stabilized under treatment are allowed*), unexplained recurrent syncope, family history of sudden death from cardiac-related causes, congestive heart failure greater than New York Heart Association (NYHA) class II, uncontrolled diabetes, uncontrolled psychiatric disorders, severe ongoing infections or any other medical condition that might be aggravated by the treatment on evaluation.
14. Prolongation of QTcF interval to greater than 480 msec.
15. History of congenital long QT syndrome
16. History of another malignancy other than the primary tumor within the last 2 years, with the exception of completely resected basal or squamous cell skin cancer or any successfully treated in-situ carcinoma, or clinically insignificant prostate cancer without any treatment intent (either

treated or on active surveillance/watchful waiting). Other cancers within the last 2 years that are considered clinically insignificant by the treating physician should be discussed with the study Sponsor to assess eligibility.

17. Known infection requiring the systemic use of, for example, an antibiotic or antiviral agent.
18. Uncontrolled intercurrent illness or psychiatric illness/social situations that would limit compliance with study requirements.
19. If female, pregnant or breast feeding.
20. Unable to swallow and retain oral medications.
21. Known contraindication to enhanced magnetic resonance imaging (MRI) and/or computerised tomography (CT) scan.

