## 11.5. Statistical Analysis

### 11.5.1. General analysis methods

The statistical analysis will be described in detail in a SAP. Any deviations from the SAP, reasons for such deviations and all alternative or additional statistical analyses that may be performed, will be described in the final report.

Ordinal and continuous data will be presented in the form of descriptive statistics, as number of subjects, mean, standard deviation, minimum, Q1, median, Q3, maximum. In addition, for PK endpoints, the geometric mean, 90% confidence interval (CIs) on geometric mean, the standard deviation of the geometric mean, and geometric coefficient of variation (CV) % will be presented.

Categorical data will be presented using contingency tables with absolute and relative frequencies.

Baseline is defined as the last measurement prior to the first study drug administration.

All data analyses will be performed using SAS® statistical software and WinNonlin® Professional.

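### Protocol 5.3.2 lets the three-times-weekly ECG follow-up end at QTcF values of 501-510 ms when baseline is 471-480 ms, above its own 500 ms trigger

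*Protocol*

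**What the plan says.** Protocol Section 5.3.2 states that significant QTcF prolongation "is defined as an interval > 500 ms or an interval which increases by 60 milliseconds (ms) over baseline". Two sets of actions follow, each after confirmation on a repeat ECG.

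- **Action A** applies if either criterion is met (above 500 ms, or a rise of more than 60 ms). The subject has ECGs at least three times a week "until the QTc interval returns to within 30 ms of baseline". In addition, "The Medical Monitor will be consulted prior to administering further doses or re-challenging".
- **Action B** applies if both criteria are met. Debio 1347 is discontinued, and ECGs at the same frequency continue "until the QTc interval return to within 30 ms of baseline".

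Under both, "If an ECG shows significant QTc prolongation the subject should be referred to a cardiologist".

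Two other provisions fix the range of baselines. Exclusion criterion 14 in Section 6.2 reads "Prolongation of QTcF interval to greater than 480 msec", so a QTcF of exactly 480 ms is eligible. Section 11.5.1 states: "Baseline is defined as the last measurement prior to the first study drug administration".

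**The concern.** The rule starts on either an absolute or a relative criterion but stops on a relative one alone. When baseline is already long, being within 30 ms of it does not bring QTcF down to 500 ms. The intensive ECG schedule can then lapse while the subject still has the value that the protocol uses to define significant prolongation.

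The subjects concerned are those with the longest eligible QTcF. Section 7.7.1 acknowledges that the drug's QTc-prolonging potential is not fully established, mentions a risk of hypokalemia, and allows other QT-prolonging drugs with caution. Once the intensive schedule ends, the fallback before Amendment 2 was an ECG on Day 28 of each cycle (Table 8-1). After Amendment 2 it is ECGs at institutional visits, required at least every two months, with none scheduled at the end-of-study visit. Enrolment has been halted, but under the Amendment 2 rationale "the Sponsor intends to continue supplying study medication to these subjects" that are judged to be benefiting.

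**Working it through.** The plan gives no figure of its own here, so the check is arithmetic on its thresholds.

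**Inputs**
- Absolute trigger: QTcF > 500 ms (Protocol 5.3.2).
- Relative trigger: rise > 60 ms (Protocol 5.3.2, actions A and B).
- Stop rule: QTcF ≤ baseline + 30 ms, no absolute limit (Protocol 5.3.2, A and B).
- Highest eligible QTcF: 480 ms (Protocol 6.2, criterion 14).

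**Condition for overlap.** The stop rule and the absolute trigger hold together when 500 < QTcF ≤ baseline + 30. This needs baseline > 470. With baseline ≤ 480 and whole milliseconds, the affected baselines are 471-480 ms. The overlap runs from 501 ms to baseline + 30, so its width is baseline − 470.

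| Baseline (ms) | Highest QTcF at which follow-up may end (ms) | Overlap with > 500 ms |
|---|---|---|
| 470 | 500 | none |
| 471 | 501 | 1 ms |
| 475 | 505 | 5 ms |
| 480 | 510 | 10 ms |

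Overlap readings are rises of between 501 − 480 = 21 ms and 30 ms, so only the absolute criterion is met there. If "within 30 ms" is read strictly (< 30), the lowest affected baseline moves from 471 to 472 ms and nothing else of substance changes.

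**Worked cases at baseline 478 ms**
- Direct: confirmed 506 ms is a rise of 28. Since 506 > 500, the subject enters A; since 28 ≤ 30, the stop condition already holds.
- Fall-back through A: confirmed 530 ms is a rise of 52, so only the absolute criterion is met. A later 506 ms (+28) ends the schedule with QTcF still above 500 ms.
- Fall-back through B: confirmed 545 ms is a rise of 67, so both criteria are met and the drug is stopped. A later 506 ms ends the schedule in the same way.

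**Search for a ceiling elsewhere.** Table 5-1 gives no QTcF value for recovery. SAP Table 3 uses 450, 480 and 500 ms only to count and flag values. Neither document contains another QTcF limit for ending the follow-up.

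**The case against.** The other side has several fair points.

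- **Wording.** A return presupposes that QTc first left the 30 ms range, so the direct case may not be what the text allows. The fall-back cases do leave the range, however, and still end above 500 ms. Nor does re-entering A on a new confirmed value above 500 ms help, because its stop condition is already met.
- **Other safeguards.** Action A requires the Medical Monitor's involvement before further dosing, B stops the drug, and any significant ECG calls for a cardiologist. Section 8.4.1 asks for follow-up by accepted medical practice after removal for an adverse event, and routine ECGs continue for subjects on treatment. All of this limits the harm. None of it states the QTcF value at which the three-times-weekly ECGs may stop.
- **Reach.** SAP Section 9.3 says the study ended earlier than expected. Amendment 2 replaces the protocol's assessments with institutional care for subjects still on drug, so it is arguable how far Section 5.3.2 still governs them. In Phase I, 3 of 58 subjects had QTc prolongation, all Grade 1 or 2 and not clinically significant. The upper 90% bound for predicted QTcF change at 80 mg was 11.44 ms, below the 21 ms minimum rise needed here. That bound is a population prediction and does not exclude individual outliers.

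The points on reach stand and reduce the urgency. They do not change what the rule permits.

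**Conclusion.** The concern holds. For eligible baselines of 471-480 ms, the intensive ECG follow-up in both A and B can end at QTcF values up to 501-510 ms, with the protocol's own > 500 ms criterion still met. The overlap is 1 to 10 ms wide; baselines of 470 ms or below are unaffected. The gap concerns the ECG schedule only, not the dosing decision or specialist referral.

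The 510 ms limit assumes that the last ECG before first dose is itself no higher than 480 ms; a longer one would widen the overlap. The number of subjects affected cannot be worked out from the documents and is probably small. The change is still worth making because it concerns patient safety and costs very little.

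**What to change.** In both A and B, end close follow-up only when QTcF is within 30 ms of baseline **and** ≤ 500 ms. The stop value becomes the smaller of baseline + 30 and 500 ms. For baselines of 471-480 ms it falls from 501-510 ms to 500 ms; for baselines of 470 ms or less nothing changes.

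One clerical edit can go with it. The definition counts a rise of 60 ms, whereas A, B and SAP Table 3 use more than 60 ms. A rise of exactly 60 ms with QTcF ≤ 500 ms is therefore significant and calls for referral, yet enters neither A nor B. Writing > 60 ms in the definition removes the mismatch; this point carries no weight in the conclusion.

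The cost is one clause in two places, one wording edit, a clarification to sites, and a few more repeat ECGs in rare subjects.

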## 6. STUDY POPULATION

Subjects with locally advanced (unresectable) or metastatic tumors with FGFR1-3 gene fusion/rearrangement who require systemic therapy and who have radiologic and/or clinical progression following at least one prior standard treatment or who have no satisfactory alternative treatment options.

### 6.1. Inclusion Criteria

Potential participants who fulfil the criteria below will be included:

1. Written informed consent given according to International Conference on Harmonisation (ICH)/Good Clinical Practice (GCP) guidelines and local regulations.
2. Cytologically or histologically confirmed advanced solid tumor.
3. Radiographic progression on prior systemic therapy; prior localized therapy (i.e., radiation, ablation, embolization) is allowed provided radiographic progression out-of-field or in the treatment field is shown.
4. Male or female  $\geq 18$  years of age.
5. Locally-advanced (unresectable) or metastatic disease harboring an FGFR1-3 gene fusion/rearrangement potentially leading to a functional FGFR aberrant protein, identified through local and/or central molecular assay.
6. The subject must have received at least one prior line of standard therapy appropriate for their tumor type and stage of disease (if available), and, in the opinion of the Investigator, s/he would have been unlikely to tolerate or derive clinically meaningful benefit from further appropriate standard of care therapy. In particular:
  - a. Biliary tract cancer subjects must have progressed on/after gemcitabine-based chemotherapy (including subjects who progressed within 6 months of gemcitabine-based adjuvant chemotherapy). Subjects can have received additional chemotherapy after documented intolerance to gemcitabine.
  - b. Urothelial cancer subjects must have progressed on/after cisplatin-based or carboplatin-based chemotherapy either given for advanced disease or within 12 months from completion if given as neoadjuvant or adjuvant therapy and anti-PD1/PDL1 therapy (unless not available, contraindicated for some reasons or refused by the subject).
  - c. NSCLC subjects must have progressed on chemotherapy and anti-PD1/PDL1 therapy (unless contraindicated for some reasons). Subjects with known EGFR mutations, ALK rearrangement or BRAF V600E mutation must have received the relevant target therapy (unless not available).
  - d. For all other tumor types, subjects must have progressed on/after appropriate standard of care (SOC) therapy (evidence-based level 1). Subjects who harbor genomic aberrations for which approved target therapy is available must have received such therapy. HER2+ or ER/PR+ breast cancer subjects should have received at least one line of HER2-targeted or ER-targeted, respectively.
7. Measurable disease according to Response Evaluation Criteria In Solid Tumours (RECIST) criteria version 1.1.
8. Eastern Cooperative Oncology Group (ECOG) (see Appendix A) performance status (PS) of 0 to 1.
9. Screening laboratory values as follows:
  - a. Absolute neutrophil count (ANC)  $\geq 1,000/\text{mm}^3$  [ $1.0 \times 10^9/\text{L}$ ].
  - b. Platelet count  $\geq 75,000/\text{mm}^3$  [ $75 \times 10^9/\text{L}$ ].

- c. Hemoglobin  $\geq 8.0$  g/dL.
  - d. Total bilirubin  $\leq 2$  x upper normal limit (UNL) [biliary stent allowed]. A subject with an isolated elevation of indirect bilirubin is eligible.
  - e. Aspartate aminotransferase (AST) and alanine aminotransferase (ALT)  $\leq 2.5$  x UNL (5 x UNL in the presence of liver metastases).
  - f. Calculated or measured creatinine clearance  $\geq 30$  mL/min (creatinine clearance measured based on 24-hour urine collection should be considered to help assess eligibility).
  - g. Serum phosphate  $< 1.5$  x UNL.
10. Female subjects of child-bearing potential must have a negative serum pregnancy test (minimum sensitivity of 25 mIU/mL) at screening and be willing to practice the highly effective contraception methods listed below from the time of study entry up to 6 months after the last day of treatment:
- a. Intrauterine device (IUD)
  - b. Intrauterine hormone-releasing system (IUS)
  - c. Bilateral tubal occlusion
  - d. Vasectomized partner
  - e. Sexual abstinence if corresponds to usual and preferred lifestyle of subject.

For hormonal contraceptives see Section 7.7.1.

**Of note:**

- Female subjects of non-childbearing potential are defined as either pre-menopausal with a documented tubal ligation or hysterectomy or post-menopausal with 12 months of spontaneous amenorrhea.
- Female subjects of child-bearing potential must refrain from donating egg(s) during the clinical study and for 6 months after Debio 1347 discontinuation.
- Male subjects must agree to use a condom from study entry and up to 6 months after the last day of treatment. The subject's female partner should use highly effective contraception methods, which may include hormonal contraceptives or any of the methods outlined above, during this period.
- Male subjects must refrain from donating sperm during the clinical study and for 6 months after Debio 1347 discontinuation.

11. Available fresh tumor sample (preferably) or, if no fresh sample can be obtained, archived tumor sample (slides or block) for central analysis of FGFR status or retrospective central confirmation in case of local screening.

**Of note:** A "liquid biopsy", e.g., ctDNA based test is acceptable for subject eligibility but then a pre-study treatment tissue sample is required for post-hoc confirmation of the fusion.

12. Life expectancy  $\geq 3$  months.

## 6.2. Exclusion Criteria

Any of the following would render a subject ineligible for inclusion:

1. History of hypersensitivity to any of the excipients in the Debio 1347 formulation (lactose hydrate, microcrystalline cellulose, croscarmellose sodium, hydroxypropyl cellulose, sodium lauryl sulfate and magnesium stearate).
2. Prior treatment with a FGFR1-3 selective inhibitor.
3. History and/or current evidence of ectopic mineralization/calcification, including but not limited to soft tissue, kidneys, intestine, myocardia, or lung, excepting calcified lymph nodes, lung nodules and asymptomatic vascular or cartilage/tendon calcifications.
4. Current evidence of clinically significant corneal or retinal disorder confirmed by ophthalmologic examination.
5. Chemotherapy, radiotherapy or small molecule anti-cancer agents within 2 weeks prior to initial dosing with Debio 1347 (3 weeks for immune checkpoint inhibitors).
6. Administration of any investigational agent within 2 weeks prior to initial dosing with Debio 1347 (3 weeks for immune checkpoint inhibitors).
7. Surgery requiring general anesthesia, except diagnostic biopsy or local procedure, within 3 weeks prior to initial dosing with Debio 1347 and/or if the subject has not fully recovered from the surgery.
8. Grade > 1 (National Cancer Institute Common Terminology Criteria for Adverse Events [NCI-CTCAE] v5.0) AEs or toxicities from previous treatments except:
  - a. Albumin ( $\geq 2.5$  g/dL is allowed).
  - b. AST and ALT in subjects with liver metastases ( $\leq 5 \times$  ULN is allowed).
  - c. Alkaline phosphatase (ALP) in subjects with bone metastases ( $\leq 5 \times$  ULN is allowed).
  - d. Any grade of alopecia is allowed.
  - e. Other Grade 1-2 clinically insignificant laboratory abnormalities are allowed.
9. Symptomatic or unstable brain metastases < 1 month (**Of note:** Subjects with asymptomatic stable and treated brain metastases are eligible).
10. Total corrected and/or ionized serum calcium  $\geq 1.5 \times$  UNL (corrected calcium =  $[0.8 \times (\text{normal albumin} - \text{subject albumin})] + \text{serum calcium level}$ ).
11. Gastro-intestinal disorders that could affect drug absorption (including, but not limited to, gastric resection, significant bowel obstruction, active ulcerative colitis, active Crohn's disease).
12. Concomitant treatment with a prohibited medication.
13. Subjects with a known history of uncontrolled or unstable angina or myocardial infarction within the last 6 months, unstable cardiac arrhythmias despite treatment (*subjects with a history of atrial fibrillation stabilized under treatment are allowed*), unexplained recurrent syncope, family history of sudden death from cardiac-related causes, congestive heart failure greater than New York Heart Association (NYHA) class II, uncontrolled diabetes, uncontrolled psychiatric disorders, severe ongoing infections or any other medical condition that might be aggravated by the treatment on evaluation.
14. Prolongation of QTcF interval to greater than 480 msec.
15. History of congenital long QT syndrome
16. History of another malignancy other than the primary tumor within the last 2 years, with the exception of completely resected basal or squamous cell skin cancer or any successfully treated in-situ carcinoma, or clinically insignificant prostate cancer without any treatment intent (either

treated or on active surveillance/watchful waiting). Other cancers within the last 2 years that are considered clinically insignificant by the treating physician should be discussed with the study Sponsor to assess eligibility.

17. Known infection requiring the systemic use of, for example, an antibiotic or antiviral agent.
18. Uncontrolled intercurrent illness or psychiatric illness/social situations that would limit compliance with study requirements.
19. If female, pregnant or breast feeding.
20. Unable to swallow and retain oral medications.
21. Known contraindication to enhanced magnetic resonance imaging (MRI) and/or computerised tomography (CT) scan.

### **6.3. Subject Replacement**

No subjects will be replaced.

## 7. CLINICAL SUPPLIES

### 7.1. Investigational Medicinal Product – Debio 1347

Composition:	Debio 1347 20 mg tablets containing the following excipients: lactose hydrate, microcrystalline cellulose, croscarmellose sodium, hydroxypropyl cellulose, sodium lauryl sulfate, and magnesium stearate.
Dosage form:	White coated tablets.
Presentation:	28 tablets in [REDACTED] blisters.
Expiry date:	Shelf life will be updated when new stability data are available.
Storage:	Mentioned on labels.

A certificate of analysis (CoA) will be provided with the product.

### 7.2. Packaging and Storage of Investigational Medicinal Product

#### 7.2.1. Packaging

Debio 1347 tablets packed in [REDACTED] blisters will be delivered to study site pharmacies by the Sponsor. Each blister will contain 28 tablets of Debio 1347 20 mg.

The site Pharmacist will deliver to the subjects the number of Debio 1347 blisters required.

#### 7.2.2. Labelling

Labelling will be open and will comply with the health authority regulations of each participating country.

#### 7.2.3. Storage

Storage conditions will be specified on the labels.

### 7.3. Dispensing and Accountability of Investigational Product

The IMP and CoA will be provided to the Investigator(s) by and under the responsibility of the Sponsor, who will also ensure release of the IMP as per current GMP (Good Manufacturing Practice) guidelines. Any documentation required by local health authorities for import of the IMP will be appropriately submitted.

The Investigator/Pharmacist at each study site will inventory and acknowledge receipt of all shipments of IMP. The IMP accompanied by analytical reports when appropriate, must be kept in a locked area with access restricted to designated study personnel and must be stored in accordance with the manufacturer's instructions.

The Investigator/Pharmacist at each study site will keep accurate records of the IMP (and other study-related drugs) dispensed. These records will specify dates and amounts dispensed, to and by whom (drug dispensing list) and report any IMP accidentally or deliberately destroyed.

At timely intervals and study closure, the IMP will be reconciled by the Sponsor's monitor/representative according to the Sponsor's standard operating procedure (SOP) unless otherwise agreed. Unused IMP will be counted and destroyed only after formal written agreement has been received from the Sponsor. Any discrepancies between the IMP returned and the expected balance must be justified.

Unused IMP must not be used for any purpose other than the present study.

